7.6 Expectedness

For investigational drugs, an AE is judged “expected” if its description agrees in nature and severity with the description of AEs previously noted with the study drug as detailed in the current Investigator’s Brochure. An “unexpected” AE is one for which the specificity or severity is neither consistent with the current Investigator’s Brochure. Spectrum will be responsible for assessing the expectedness of AEs.

7.7 Serious Adverse Events

In the interest of patient care and to allow Spectrum to fulfill all regulatory requirements, SAEs are to be reported to Spectrum within 24 hours of knowledge of the event. SAEs are defined

(21 CFR 312.32, ICH of Technical Requirements for Registration of Pharmaceuticals for Human Use E2A Guideline) as those AEs that meet any of the following criteria:

- Results in death
- Is life-threatening (Grade 4): ie, any event that, in the opinion of the Investigator, poses an immediate risk of death from that event
- Requires inpatient hospitalization or prolongation of existing hospitalization (excluding hospitalizations for study therapy, disease-related procedures, or placement of an indwelling catheter, unless associated with other SAEs)
- Results in a persistent or significant disability/incapacity
- Results in a congenital anomaly/birth defect
- Includes important medical events that may not be immediately life threatening or result in death or hospitalization but may jeopardize the patient or may require intervention to prevent one of the outcomes listed in this definition

Adverse events that do not meet any of the above criteria for serious should be regarded as non-serious.

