1.3.2 Clinical Safety of Qapzola

The majority of data establishing the safety of a single intravesical instillation of Qapzola in the post-TURBT setting came from the two placebo-controlled pivotal studies, SPI-611 and SPI-612 (N=808). The median duration of each study was ~2 years.

The incidence and type of adverse events (AEs) reported in SPI-611 and SPI-612 was similar for both treatment groups. Regardless of treatment group, approximately 80% of patients in each study experienced at least one treatment-emergent AE (TEAE); most TEAEs (70% to 80%) were of Grade 1 or Grade 2 severity. The most common TEAEs (occurring in approximately 10% to 20% of patients in either treatment group in either study) were dysuria, urinary tract infection, hematuria, and pollakiuria with less common TEAEs (5% to 10% of patients) being micturition urgency, bladder pain, urinary retention, procedural pain and bladder spasm.

Few patients (10% to 13%) had TEAEs the investigator considered treatment related with the incidence of these AEs being similar between Qapzola and placebo. The most common treatment-related AEs (occurring in 1% to 5% of patients) were dysuria, bladder spasm, micturition urgency, bladder pain, hematuria, urinary tract infection, and pollakiuria.

Approximately 25% of patients in SPI-611 and SPI-612 reported a serious adverse event (SAE), with the incidence and types of SAEs reported being similar between studies and between treatment groups. The most common SAEs (in <3% of patients) were congestive cardiac failure, hematuria, urinary retention, atrial fibrillation, chronic obstructive pulmonary disease, pneumonia, knee arthroplasty, and coronary artery disease, most of which may be expected in an elderly population. Two patients experienced SAEs that were considered to be possibly related to Qapzola. Both SAEs started on the day of study drug instillation, and both resolved: one patient had Grade 3 hematuria and recovered within 3 days, the other had Grade 3 acute renal failure and recovered within 18 days. Another patient who received Qapzola died of acute renal failure 624 days after Qapzola treatment; the event was assessed as not related to study treatment. Hematuria is a common presenting sign of NMIBC [5, 13] and is an expected consequence of the TURBT procedure.

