Since there was only one instillation, there were no AEs that led to discontinuation of study drug instillation. Approximately 4% of patients discontinued from the studies due to AEs over the 2-year study period, with the incidence of these AEs being similar between studies and between treatment groups, and no individual AE occurring in more than 1% of patients. None of the AEs leading to discontinuation were assessed as related to study treatment by the Investigator.

Approximately 3% of patients had AEs that resulted in death, none of which the investigator assessed as related to study drug (Qapzola or placebo). There were no deaths reported in the immediate post TURBT instillation period (within 30 days).

Clinical laboratory assessments showed no clinically meaningful differences between patients receiving Qapzola and placebo in any hematologic, liver, kidney, or metabolic parameters and in a subgroup of patients in SPI-611 (n=191), there was no measurable effect on functional bladder capacity.

Data from the other six studies were supportive of the safety data in SPI-611 and SPI-612. Among the 245 patients in these studies, 139 received multiple instillations of Qapzola. The types of TEAEs in these patients were similar to those in SPI-611 and SPI-612, although the incidence of dysuria, hematuria, pollakiuria, and micturition urgency tended to be higher in

patients receiving multiple instillations of Qapzola (~15% to 45%) than single instillations (~3% to 15%). Treatment-related SAEs were experienced by three patients who received single instillations of Qapzola (pelvic pain, postoperative urinary retention, and hematuria) and four patients receiving multiple instillations of Qapzola (dysuria, hematuria and hemorrhage urinary tract, chemical cystitis, pollakiuria); all patients recovered. No patients in the supportive safety studies discontinued due to AEs and none died.

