6.2 Dose, Route of Administration, and Schedule of Study Drug

6.2.1 Dose and Route of Administration of Study Drug

Randomized patients will receive either Qapzola 8 mg in 50 mL of dose solution or matching placebo. Reconstitution and dose preparation procedures are outlined in the Pharmacy Manual. The 50 mL dose solution of study drug is to be instilled into the bladder via an indwelling 100% Silicone Foley catheter, where it is to be retained for 60 ± 5 minutes.

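### Protocol 7.7 allows an unplanned admission for catheter-managed urinary retention to be recorded as non-serious, and the SAP defines a serious event differently

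*Protocol*

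**What the plan says.** Protocol 7.7 lists six seriousness criteria. The hospitalization criterion covers inpatient admission or prolongation of an existing stay, with this qualification: "excluding hospitalizations for study therapy, disease-related procedures, or placement of an indwelling catheter, unless associated with other SAEs". The last criterion is a judgement-based one: "Includes important medical events that may not be immediately life threatening or result in death or hospitalization". The section closes with a default: "Adverse events that do not meet any of the above criteria for serious should be regarded as non-serious".

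Protocol 7.7.2 separately states that planned and prescheduled hospitalizations are not SAEs. Protocol 7.7.1 requires SAEs to be reported to the sponsor within 24 hours of knowledge. Under Protocol 7.1 the investigator assigns seriousness.

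The only indwelling catheter that the protocol names is the bladder catheter through which study drug is given: in section 6.2.1 the dose is "instilled into the bladder via an indwelling 100% Silicone Foley catheter".

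On earlier experience, Protocol 1.3.2 says of SPI-611 and SPI-612: "The most common SAEs (in <3% of patients) were congestive cardiac failure, hematuria, urinary retention", followed by other conditions. For the six supportive studies it reports treatment-related SAEs in "three patients who received single instillations of Qapzola (pelvic pain, postoperative urinary retention, and hematuria".

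SAP 7.3.3 defines an SAE by death, life threat, required or prolonged hospitalization, disability, or congenital anomaly. It has no catheter exclusion and no important-medical-event criterion. SAP 1 says that the SAP supersedes definitions in other documents for the statistical analyses. SAP 2.1 leaves safety as the only objective.

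**The concern.** In a trial of intravesical treatment after bladder surgery, catheterization is the obvious response to retention or clot obstruction. A seriousness rule that sets aside admissions for catheter placement therefore touches one of the local events that the safety analysis ought to count reliably. A site that applies the rule literally can mark an unplanned admission for retention as non-serious. It then sends no 24-hour report, and the event is missing from the SAE listing and the SAE line of the overall summary.

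No other rule singles the event out. The AEs of special interest in the Protocol synopsis are dysuria and hematuria of grade 3 or higher; retention is not among them. The dose is 8 mg, against 4 mg in SPI-611 and SPI-612, so rates from those trials cannot simply be carried over. With all efficacy analysis removed, the SAE output is one of the few results that the trial will report.

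**Working it through.** The point rests on wording, and the plan gives no figure to reproduce. The check sets the definitions side by side and then asks how many events could be involved.

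**1. Scope of the exclusion.** Protocol 7.7.2 already removes planned admissions. The exclusion in 7.7 does not mention planning. Unless it merely repeats 7.7.2, it also reaches unplanned admissions. It names hospitalizations, whereas the criterion also covers prolongation of a stay, so whether a prolonged Day 1 stay is excluded is unclear.

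**2. Three events under each definition.**

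| Event | Protocol 7.7 | SAP 7.3.3 |
|---|---|---|
| Unplanned admission for retention, relieved by catheter, nothing else | Hospitalization criterion can be read as not met; serious only if judged an important medical event | Serious (hospitalization) |
| Retention without admission, judged an important medical event | Serious | No criterion met |
| Unplanned admission for retention together with another SAE | Serious | Serious |

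The first two rows disagree, in opposite directions.

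**3. Which definition drives the output.** Sites flag seriousness under the protocol. SAP 7.3.3 lists and counts SAEs but describes no step that re-derives seriousness from the AE record. Sponsor drug safety review (Protocol 9.4.2) assesses each SAE, which means events already reported as such. The wider hospitalization wording in the SAP therefore does not by itself recover an event that a site marked non-serious.

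**4. What remains recorded.** Retention within 35 days of dosing is still a treatment-emergent AE, tabulated by preferred term and grade and listed (SAP 7.3.1).

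**5. Size, for context only.**

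- Supportive studies: "Among the 245 patients in these studies, 139 received multiple instillations of Qapzola". So 245 − 139 = 106 others. Assume that each of the 106 had one Qapzola instillation. Treatment-related retention SAEs: 1/106 = 0.9%. Exact 95% limits are the 2.5% point of Beta(1, 106) and the 97.5% point of Beta(2, 105): 0.02% and 5.1%.
- Planned Qapzola arm: 500 × 2/3 ≈ 333. Expected events: 333 × 1/106 ≈ 3.1, with range 333 × 0.00024 ≈ 0.1 to 333 × 0.0514 ≈ 17.
- Ceiling from SPI-611/612: 3% × 500 = 15 patients over both arms.

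These figures use the planned size, which was not reached (SAP 4.2). They also count retention SAEs whatever made them serious, not only admissions for catheter placement. The 3% is an all-cause ceiling from trials with a median duration of about 2 years, whereas Protocol 7.7.1 collects all SAEs here only to Day 35 and procedure-related ones thereafter. None of them estimates the number affected.

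**The case against.** The best counter-argument is that the exclusion concerns admissions for a procedure, while Protocol 7.2 treats the condition that leads to a procedure as the AE. On that reading retention is the event, the catheter is only its treatment, and the clause covers study and disease procedures, among which it is listed. The overlap with 7.7.2 may be simple redundancy. The exclusion also limits only one of six criteria. The important-medical-event criterion includes events needing intervention to prevent a listed outcome, and catheterization for acute retention could fit that. The exception for association with other SAEs remains, and the SAP definition has no exclusion at all.

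This narrows the point without removing it. The wording supports both readings, so sites may differ. The important-medical-event route relies on individual judgement against an explicit exclusion. The SAP wording helps only if someone reapplies it to the AE data.

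A reader might infer more than the documents support:

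- **That retention must be recorded as non-serious.** It can be; other criteria may still apply.
- **That retention was a treatment-related SAE in SPI-611 or SPI-612.** The two possibly related SAEs there were hematuria and acute renal failure. The related retention SAE was one patient in the supportive studies. Protocol 1.3.2 also describes the incidence and types of SAEs in SPI-611/612 as similar between treatment groups.
- **That the SAE rate can no longer be compared with SPI-611/612 because of this clause.** The documents do not give the SAE definition used in those trials, so this cannot be claimed.

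**Conclusion.** The point holds as a defect in classification and a conflict between the two documents. Under Protocol 7.7 an unplanned admission for urinary or clot retention managed by catheter can lose SAE status. SAP 7.3.3 would class the same admission as serious but contains no step to restore it. SAE status, expedited reporting and the SAE count are at risk; the AE record is not.

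The number affected is unknown and probably small. The planned-size figures (about 3 treatment-related events on Qapzola, range 0.1 to 17; at most 15 patients from the 3% ceiling) should not be read as estimates, because recruitment stopped short and not every retention SAE is an admission for catheter placement. Calling the number small assumes that retention at 8 mg is not much more frequent than in the earlier studies, which the documents cannot confirm. The conclusion also assumes that at least some sites read the exclusion literally. The correction is still worth making, because safety is all that this trial will report and the check is cheap.

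**What to change.** - Reconcile Protocol 7.7 with SAP 7.3.3, including the important-medical-event criterion that the SAP leaves out, and state in the report which definition the SAE output uses.
- Before that output is run, or rerun if it already exists, query the recorded AEs for unplanned or prolonged admissions for retention, clot evacuation or catheterization. Review the seriousness of each one without reference to treatment arm.
- In the protocol and CRF completion guidelines, limit the exclusion to the protocol-mandated Day 1 catheterization and to admissions planned before dosing. Say explicitly whether prolongation of a stay is covered. As the study has been terminated, this change mainly serves any later study that reuses the text; for this trial the query is the effective remedy.

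The cost is one data query and a sentence or two of text. The reported SAE rate may become slightly less favourable. None of this alters how patients are managed.

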7.7.1 Serious Adverse Event Reporting

From the time the Informed Consent is signed until Day 1 of the study, only SAEs related to study procedures will be recorded. All SAEs that occur from the first dose of study drug administration until Day 35 (± 5 days) post-TURBT will be recorded. All SAEs related to study procedures will be recorded for the remainder of the follow-up period and are to be reported to Spectrum within 24 hours of knowledge of the event.

SAEs are to be reported and the serious adverse event report (SAER) faxed or emailed within 24 hours of knowledge of the event to:

Spectrum Pharmaceuticals, Inc.
Primary Contact: Pharmacovigilance Department
Fax: [REDACTED]
E-mail: [REDACTED]

Spectrum or its designee may request additional information from the Investigator to ensure the timely completion of accurate safety reports. Safety data that are critical to the reportability of an SAE, such as causality assessment and serious criteria, should be included in the initial faxed SAER. If omitted, a timely response to drug safety data queries received from Spectrum or a Spectrum designee is expected.

The Investigator is to take all appropriate therapeutic measures necessary for resolution of the SAE. Any medications necessary for treatment of the SAE are to be recorded in the concomitant medication section of the patient's CRF.

SAEs that are study-treatment related will be followed until resolution or until they have returned to Baseline/Grade 1, whichever is longer, or until it is determined that the outcome will not change with further follow-up.

Additionally, the SAE is to be entered in the AE section of the CRF. Follow-up SAERs need to be submitted to Spectrum within 24 hours, once additional information regarding the event becomes available (eg, diagnosis is made, laboratory or test results, event course, outcome, etc).

Spectrum/designee will be responsible for reporting SAEs to the regulatory authorities in accordance with applicable expedited reporting regulatory guidelines. The Investigator is responsible for submitting SAEs to his/her Institutional Review Board (IRB)/Ethics Committee (EC). Copies of each SAER, and documentation of IRB/EC notification and acknowledgement of receipt, will be kept in the Site's Regulatory Binder.

7.7.2 Exclusions to Serious Adverse Event Reporting Requirements

The following are not considered SAEs:

- Situations where an untoward medical occurrence did not occur (eg, social and/or convenience admission to a hospital, hospitalization for diagnostic tests such as CT scans)
- Anticipated day-to-day fluctuations of pre-existing disease(s) or condition(s) present or detected prior to first study treatment administration that do not worsen
- Planned and prescheduled hospitalizations and procedures
- Progressive disease

7.8 Reproductive Risks

To date, there are no adequate and well-controlled studies of Qapzola in pregnant women. Because the reproductive risks have not been studied in pregnant women, Qapzola is not recommended for use during pregnancy.

Pregnancies involving a study patient or a patient's partner, that occur from the first dose of study treatment through 35 days after the last dose of study treatment, must be reported within 24 hours after the Investigator has gained knowledge of the event via fax or e-mail (see contact information in [Section 7.7.1](#)). Follow-up information regarding the outcome of the pregnancy will be requested by the Spectrum Pharmacovigilance Department.

All patients who become pregnant during participation in this study are to be withdrawn from the study.

8 STATISTICAL DESIGN AND ANALYSIS

This section contains a brief overview of the statistical analyses planned for this study including the pre-specified power and sample size calculation as well as the methods for the primary endpoint analysis. A formal statistical analysis plan (SAP) will be finalized before database lock.

8.1 Sample Size

The enrolled patients will be randomized in a 2:1 ratio to either Qapzola or placebo. The primary endpoint is Time to Recurrence in the Target Population. The primary endpoint analysis involves a test of comparison: 8 mg Qapzola vs. placebo using 2-sided log-rank test at 5% level of significance.

The sample size calculation assumes a hazard ratio (HR) of 0.65 based on the results from previous Phase 3 studies of Qapzola and placebo comparisons overall and in the drug instillation time window 31-90 minutes post-TURBT as described in [Section 1.3.1.2](#) and [Section 1.3.1.4](#) respectively.

Approximately 500 patients will be enrolled and treated in this study. Accrual time is estimated as 24 months and follow-up time as 24 months. For the sample size calculation, the HR of 0.65 is assumed for the improvement in time to recurrence in favor of Qapzola as compared to the Placebo with a hazard rate of 0.3. In a 2:1 randomization of Qapzola and Placebo, sample sizes of 425 Target disease patients (284 in Qapzola and 141 in Placebo) will provide 85% power. This sample size is estimated to provide a total of 208 recurrence events during the follow-up duration of at least 24 months. The sample size calculation was based on PASS 14 (NCSS, LLC, Kaysville, Utah).

Since the Target population is confirmed by pathology review and this will be performed after patients are randomized and have undergone TURBT procedure, the study will account for misclassification in the Target disease population. Accounting for 15% misclassification of randomized patients, the study will enroll approximately 500 patients. However, the study will continue to enroll patients until the required number of Target disease patients are accrued.

A futility analysis will be performed during the study conduct to determine the study continuation. The futility analysis will be conducted in the Target patients once 60 events are observed. The study will be stopped for futility if the calculated z-value from the log-rank test of HR is >1.0 . No adjustment for multiplicity of comparison will be made for futility analysis and the final analysis will be performed at 5% level of significance.

At the time of futility analysis, the decision will be made if additional subjects should be recruited to ensure that enough events would be accumulated at approximately 2-year follow-up from drug instillation. Based on the expected events of 208 out of 425 subjects after 2-year follow-up, it is anticipated that the first 123 subjects should have completed 2-year follow-up at the time of the futility analysis. However, if lower overall recurrence rate is observed, additional patients in the Target Population will be recruited in order to accrue the required number of events.

The futility analysis for the decision of study continuation and adjustment to sample size will be performed by the IDMC that will have access to the unblinded data. The study team will be blinded to the treatment allocation during the follow-up period.

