Approximately 500 patients will be enrolled and treated in this study. Accrual time is estimated as 24 months and follow-up time as approximately 24 months. For the sample size calculation, a hazard ratio (HR) of 0.65 is assumed for the improvement in Time to Recurrence in favor of Qapzola as compared to the placebo with a hazard rate of 0.3 in placebo arm. In a 2:1 randomization of Qapzola and placebo, sample sizes of 284 in APZ and 141 in PBO Target disease patients (total of 425) will provide 85% power. This sample size is estimated to provide a total of 208 recurrence events during the follow-up duration of at least 24 months. The primary analysis will be conducted once a total of 208 recurrence events are observed. The events will be monitored in a blinded fashion regardless of the treatment assignment to determine the timing of the primary analysis. All secondary endpoint analyses will be conducted at the time of the primary analysis.

Since the Target population is confirmed by the pathology review and this will be performed after patients are randomized and have undergone TURBT procedure, the study will account for misclassification in Target disease population. Accounting for 15% misclassification of randomized patients, the study will enroll approximately 500 patients. However, the study will continue to enroll patients until the required number of Target disease patients are accrued.

A futility analysis will be performed during the study conduct to determine the study continuation. The futility analysis will be conducted in the Target patients once 60 events are observed. The study will be stopped for futility if the calculated z-value from the log-rank test of HR is >1.0 . No adjustment for multiplicity of comparison will be made for futility analysis and the final analysis will be performed at 5% level of significance.

The interim analysis will also be used to determine if additional subjects should be recruited to ensure that enough events would be accumulated at approximately 2-year follow-up from drug instillation. Based on the expected events of 208 out of 425 subjects after 2-year follow-up, we anticipate that the first 123 subjects should have completed 2-year follow-up visits at the futility analysis when 60 events are observed. However, if lower

[figure not shown]
overall recurrence rate is observed, additional patients in the Target Population will be recruited in order to accrue required number of events.

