6.5 Treatment Blinding Procedures

This study is double-blind with respect to treatment assignment; all study participants (ie, subject, study staff including the physician, and all non-study individuals) and the Sponsor remain blinded until the study is complete and unblinded. An independent data monitoring committee (IDMC) will be established to review safety data for the first 30 treated patients in the study. The IDMC will also conduct the futility analysis of the unblinded data as described in [Section 8.1](#). The details for the IDMC will be provided in a separate Charter. An IWRS will be set up with appropriate access structure in order to keep the above study team blinded. Pharmacy will have access to the IWRS to get the treatment allocation.

The patients enrolled in this study will be randomized in a 2:1 ratio to either:

- **Arm 1:** one instillation of 8 mg Qapzola
- **Arm 2:** one instillation of placebo

In the case of a significant safety concern, a patient's treatment may be unblinded. The Investigator should first contact the Medical Monitor immediately to discuss and agree on the merits and need for unblinding a patient's treatment. The reasons and rationale for breaking the treatment blind will be documented in writing and maintained in the study file.

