8.5.5 Primary Endpoint - Time to Recurrence

The Time to Recurrence is defined as time from Day 1 treatment to the date of the first histologically confirmed recurrence as described in [Section 8.5.1](#) above. Patients without a recurrence at the time of the primary analysis will be censored at the last available date of cystoscopy. Patients who died due to any cause before confirmed recurrence will be censored at the last available date of cystoscopy.

The primary analysis will be conducted using a hierarchical procedure of hypothesis testing at a 5% level of significance. The primary endpoint, Time to Recurrence, will be examined first, and if significant, the secondary endpoint, 2-Year Recurrence Rate, will be examined next, and if also significant, Extent of Disease at Recurrence, and Time to Disease Progression will then be examined.

The primary endpoint of Time to Recurrence will be analyzed using the Target Population as defined in [Section 8.3](#). The primary analysis of Time to Recurrence will be conducted once a total of 208 recurrence events are accrued in the study. The primary endpoint analysis involves a 2-sided log-rank test of time to recurrence between two treatment groups at 5% level of significance. Distribution of Time to Recurrence will be estimated using the Kaplan-Meier product-limit method. The median times to recurrence with two-sided 95% confidence intervals (CI) will be estimated, together with the estimates at 6, 12, 18 and 24 months. The hazard ratio and corresponding 95% CI of the treatment effect will be estimated from a Cox proportional hazard regression model with treatment arm as the only covariate and tested using a likelihood ratio test at the level of significance described above. Additional exploratory analysis of Cox proportional hazard regression will be used to estimate the hazard ratio and its 95% CI. The model will include treatment effect, study center, low vs intermediate risk, primary vs. recurrent disease as stratification factor in addition to any other baseline or demographics factors.

In addition, the following additional sensitivity analyses of Time to Recurrence will be provided:

- a. Excluding patients who miss 2 consecutive cystoscopies or lost to follow-up either prior to recurrence or prior to the date of the primary analysis – Completer analysis

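### Expecting 123 patients with 2 completed years at the 60-event futility look does not follow from the protocol's inputs: 208/425 is the month-48 total, and at 60 events few or none will have reached 2 years.

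*Protocol*

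**What the plan says.** Section 8.1 sets out the design: "Accrual time is estimated as 24 months and follow-up time as 24 months", a hazard ratio of 0.65, a placebo hazard of 0.3 with no time unit, and 425 Target patients (284 Qapzola, 141 placebo) for 85% power. Of the event total it says: "This sample size is estimated to provide a total of 208 recurrence events during the follow-up duration of at least 24 months".

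Later in the same section, on the futility analysis at 60 events, the 208 returns as a 2-year figure: "Based on the expected events of 208 out of 425 subjects after 2-year follow-up, it is anticipated that the first 123 subjects should have" reached the end of two years by then. The Synopsis (Statistical Methods) has the same statement with the trigger spelled out: "we anticipate that the first 123 subjects should have completed 2-year follow-up visits at the futility analysis when 60 events are observed".

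Both places put this expectation between the question of adding patients and the stated condition for doing so: "if lower overall recurrence rate is observed, additional patients in the Target Population will be recruited". Neither gives a numerical value for that condition.

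Section 3.2 gives a different timetable, 2.5 years of accrual plus about 2.5 years of follow-up. It is used below as a sensitivity case.

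**The concern.** The same 208 appears once as the yield of follow-up lasting at least 24 months and once as the yield after 2 years. With staggered entry these are different quantities: when the last patient reaches 2 years, the first has been followed for nearly 4.

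The 123 looks like 60 divided by 208/425. That division treats the 60 events as coming only from patients who have finished 2 years, whereas every enrolled Target patient contributes events from Day 1.

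At stake is how the committee reads the interim data when deciding on extra recruitment. The only figures printed beside that decision are 49% at 2 years and 123 completers. If both are wrong, an on-plan trial can look slow.

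**Working it through.** **Inputs** (Section 8.1): placebo hazard 0.3; Qapzola hazard 0.65 × 0.3 = 0.195; 141 and 284 patients; accrual R = 2 years; further follow-up F = 2 years. **Assumptions not in the documents:** hazard per year, exponential times, uniform accrual, no dropout.

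**1. Reproduce 208.** For one arm with hazard λ, P(event by R + F) = 1 − [exp(−λF) − exp(−λ(F + R))]/(λR).
- Placebo: 1 − (0.5488 − 0.3012)/0.60 = 0.587; × 141 = 82.8
- Qapzola: 1 − (0.6771 − 0.4584)/0.39 = 0.439; × 284 = 124.8
- Total **207.6**, matching 208 at study month 48.

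The unit is well supported. Reading 0.3 per 2 years gives 122 events, and reading it as a 30% annual probability gives 233. Per year also implies 1 − exp(−0.6) = 45.1% placebo recurrence at 2 years, close to the pooled 45.5% in Table 1 (Section 1.3.1.1).

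**2. Yield at exactly 2 years per patient.**
- Placebo: 141 × (1 − exp(−0.60)) = 141 × 0.451 = 63.6
- Qapzola: 284 × (1 − exp(−0.39)) = 284 × 0.323 = 91.7
- Total **155.3 of 425 = 36.5%**, against 208/425 = 48.9%; a difference of 52.7 events.

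To reach 208 by 2 years per patient, the placebo hazard would have to be about 0.445 per year. Also, 48.9% for both arms combined exceeds the overall placebo-arm rate in each earlier Phase 3 trial (44.6% and 46.3%, Table 1).

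**3. Where 123 comes from.** 60/(208/425) = 122.6. Even on this completers-only logic, the correct yield gives 60/0.365 = 164. The expected number of 2-year recurrences among the first 123 patients is 123 × 0.365 = 45, not 60.

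**4. When 60 events arrive.** For t ≤ R, expected events = Σ (N/R) × [t − (1 − exp(−λt))/λ].

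| Accrual | t at 60 events | Placebo + Qapzola | Enrolled | Past 2 years |
|---|---|---|---|---|
| 24 months | 20.1 months | 25.2 + 34.8 | 355 | 0 |
| 30 months | 22.6 months | 25.1 + 34.9 | 320 | 0 |

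If recurrence is detected only at scheduled cystoscopies (simulated), the times become 21.5 and 24.1 months, with means of 0.2 and 8.5 patients past 2 years (95% range 0 to 41 for the latter). Slower uniform accrual at the design hazards never gave more than about 90 completers in the range tried. If 48.9% at 2 years were true, 60 events would come sooner still (month 16.7 or 18.9), again with no completers.

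**5. The reverse check.** 123 patients have passed 2 years at month 30.9 (24-month accrual) or 32.7 (30-month). By then the design expects about 126 or 117 events. For only 60 to have occurred, both hazards would have to be 0.425 or 0.460 times the design values.

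**6. A usable design rate.** Person-years at month 48: 82.8/0.3 + 124.8/0.195 = 915.9, so the pooled rate is 207.6/915.9 = 0.227 per year. At 60 events it is 60/262.5 = 0.229. With scheduled detection and exposure counted to recurrence or last cystoscopy, the simulated 95% range at 60 events is about 0.18 to 0.29 at hazard ratio 0.65.

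**The case against.** **The 2-year phrase has a benign reading.** If it means the end of the 24-month follow-up phase, 208/425 is correct. That is fair, although Section 8.1 also speaks of about 2 years from drug instillation, which points to follow-up per patient. The inference to 123 fails either way.

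**The 123 is an anticipation, not a decision rule.** This stands. The stated condition is a lower overall recurrence rate. A reader might infer that a slow trial with 123 completers would pass as on plan and reach its 208th event at about month 93 to 96 instead of 48 to 51. The documents do not support that. At hazards of 0.425 or 0.460 times design, the 2-year recurrence would be about 18% or 19%, far below the 49% the protocol expects, so the stated condition would be met. The delay also assumes that no patients are added and nobody acts on event counts, yet the Synopsis says "The events will be monitored in a blinded fashion regardless of the treatment assignment to determine the timing of the primary analysis".

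**A trigger may exist elsewhere.** Section 6.5 says "The details for the IDMC will be provided in a separate Charter". The Charter is not available here and may define a threshold.

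**The interim was never used.** The SAP removed it, with all efficacy analyses, after early termination. The point therefore concerns the protocol's design and not the final analysis.

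**Conclusion.** The benchmark is wrong as written. On the stated inputs, the 2-year yield is about 155/425 (36.5%); 208 belongs to about month 48; and at 60 events roughly 320 to 355 Target patients will be enrolled with none or few past 2 years. These figures rest on a yearly hazard, exponential times, uniform accrual and no dropout.

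The direct practical risk is a false shortfall: a trial running to plan at about 37% would be read against 49%, which could prompt needless recruitment. Conversely, 123 completers at 60 events would mean a trial running at less than half the design hazard, not one on schedule.

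A reader might also infer that the trial is underpowered or its event target miscounted. It is not: 208 reproduces, and alpha, the stated power, the 60-event trigger and the primary log-rank test do not depend on the 123. The point is worth correcting because it sits beside a design decision and costs almost nothing to put right.

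**What to change.** In Section 8.1 and the Synopsis:

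- State about 155 events (36.5%) at 24 months per patient, and 208 at about month 48, or about month 51 if accrual takes 30 months. Print the unit of the 0.3 hazard.
- Delete the 123-completer sentence, or replace it with the expected position at 60 events: about month 20 with about 355 Target patients enrolled, or about month 23 with about 320.
- Say that a lower overall recurrence rate is judged against the design value: about 37% at 2 years by Kaplan-Meier, or about 0.23 pooled events per person-year. Count exposure to match the primary rule: "Patients without a recurrence at the time of the primary analysis will be censored at the last available date of cystoscopy".
- State beside it that this value assumes a hazard ratio of 0.65, is imprecise at 60 events (about 0.18 to 0.29), and moves with the true effect. At a hazard ratio of 0.44, the SPI-611 result for the 31 to 90 minute window in Section 1.4, the lower end falls to about 0.14. At a ratio of 1 the range starts at about 0.23. A low pooled rate can therefore reflect a strong drug effect, and a moderate shortfall cannot be told apart reliably.

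The cost is wording only, with no extra patients or data. The downside is that the stated maturity of the interim becomes less favourable: few or no patients, not 123, will have 2 years of follow-up.
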